2.6 Trabectedin - Commercially Sourced

Trabectedin is an FDA approved synthetic, marine-derived alkylating agent discovered in a high through-put screen of compounds from the Caribbean tunicate, *Ecteinascidia turbinata*²⁰. With limited systemic therapy options available for sarcomas as a whole, trabectedin has the opportunity to be significantly beneficial for subjects with metastatic disease. Evidence shows that disruption of DNA by trabectedin ultimately causes apoptosis and sensitization of cell lines to Fas-mediated cell death²¹.

Multiple studies, including specific experiments in soft tissue sarcomas, have also validated that trabectedin works at the level of the tumor microenvironment with selective activity against monocytes and tumor-associated macrophages^{22,23}. The inhibition of these immune factors allows for the prevention of angiogenesis and further disease progression^{24,25}. Deprivation of inflammatory-mediated support in the tumor microenvironment may be one of the most important aspects of trabectedin's mechanism of action, making the drug efficacious as a cancer treatment. Other mechanisms for the chemotherapeutic actions of trabectedin may include modulation of the cell cycle and interaction with transcription factors^{26,27}.

Phase I Trials

A number of Phase I trials have assessed differential dosing and infusion schedules for the administration of trabectedin²⁸⁻³⁴. Results from these studies have established the optimal regimen of administration to be a 1.5 mg/m² infusion over 24 hours every 3 weeks³⁵. Notably, Taamma and colleagues performed a Phase I trial of trabectedin in 52 subjects with treatment refractory tumors that recommended the current optimal dosing schedule of 1.5 mg/m² for a 24-hour continuous infusion³¹. The most prevalent dose limiting toxicities in the study were hematological in nature. At the recommended dose, severe neutropenia was reported in 33% of cycles, severe thrombocytopenia in 10% of cycles and reversible, but severe, elevations in transaminase levels in 38% of cycles.

Combination therapies of trabectedin with other chemotherapeutic agents including gemcitabine, doxorubicin, doxil, and cisplatin have also been assessed in Phase I trials³⁶⁻⁴¹. The most promising results from these studies in sarcoma subjects have been from the trials administering trabectedin in combination with doxorubicin. One of the trials showed a response rate (RR) of 18% and stable disease in 56% of soft tissue sarcoma subjects (n=29)⁴⁰. None have seen significant safety concerns.

Based on these studies, the US, standard starting dose is 1.5mg/m² – this is noted in the trabectedin package insert, however around the world standard dosing varies. In Japan, the standard starting dose is 1.2 mg/m² as this was the MTD they found on a phase I trial they performed.¹⁹ The DLTs observed on the Japanese phase I at the 1.5 mg/m² dosing were LFT abnormalities.

Phase II Trials

Two Phase II trials in 2004 provided the initial analysis of trabectedin in soft tissue sarcomas. The first of these studies was run on 54 pretreated soft tissue sarcoma subjects, and reported a low response rate of 4%, but a high disease control rate at 6 months of 24%⁴². Trabectedin was administered at a dose of 1.5 mg/m², over 24 hours every 3 weeks. Approximately half of

the subjects in the study eventually developed grade 3/4 AST and ALT levels. Another common adverse event was fatigue, being grade 3/4 in 15% of subjects. In this trial, 4 subjects (7.4%) discontinued trabectedin due to adverse events. In addition, there were two treatment-related deaths, both were subjects who developed acute renal failure.

The second Phase II trial, published in 2004, again reported a low response rate of 8% and a one year overall survival rate of 53% in 36 previously treated sarcoma subjects⁴³. This study also utilized the same dosing schedule of trabectedin (1.5 mg/m², over 24 hours every 3 weeks). The toxicity profile of the drug was similar to previous trials with subjects experiencing elevations in transaminases, fatigue and hematological toxicity. Growth factors such as, G-CSF, can be administered to help prevent hematological toxicity, however a recent retrospective study showed that G-CSF administration has only been used in about 10% of Phase II trials of trabectedin in solid tumors⁴⁴.

Early promising results in these Phase II studies led the European Organization for the Research and Treatment of Cancer (EORTC) to initiate a Phase II trial of trabectedin in 104 subjects treated in the second and third-line setting⁴⁵. This trial also reported a low response rate of 8%. The 6-month PFS was 29% and the median overall survival (OS) was reported as 9.2 months. Subsequently, a further Phase II trial in 36 subjects was run to evaluate the activity of trabectedin in the first-line setting. The overall response rate was reported as 17%, and the 1-year PFS and OS rates were 21% and 72%, respectively⁴⁶. This study also importantly concluded that trabectedin has similar ranges of objective responses and overall survival rates in the first-line setting to the two most active drugs in soft tissue sarcomas: doxorubicin and ifosfamide.

Demetri and colleagues performed a Phase II trial randomizing 270 subjects with leiomyosarcoma and liposarcoma to receive either 1.5mg/m² of trabectedin over 24 hours every 3 weeks, or 0.58 mg/m² over 3 hours every week for 3 out of 4 weeks⁴⁷. Subjects were required to have experienced documented disease progression while on doxorubicin and ifosfamide prior to trial entry. The 24-hour infusion schedule showed a significantly longer median time to progression (TTP) (3.7 vs. 2.3 months) and PFS at 6 months (3.3 vs. 2.3 months) as compared to the 3-hour infusion schedule. No significant difference in overall survival was observed between the two arms of the trial, however, there was a strong trend favoring the 24-hour infusion schedule (13.9 months vs. 11.8 months). Trabectedin was generally well tolerated in this study, with the most frequently reported grade 3/4 adverse events being neutropenia and elevated transaminases. Febrile neutropenia occurred in 1% of subjects, and the majority of adverse events were mild to moderate. There was also no documentation of cumulative toxicities. Another Phase II trial recommended the use of trabectedin as a neoadjuvant therapy for subjects with advanced myxoid liposarcoma⁴⁸.

The results of these Phase II trials led to licensing approval of trabectedin by the European Union for advanced soft tissue sarcoma in 2007, and the drug is now approved in over 70 countries.

Phase III and FDA Approval

The Phase III trial of trabectedin vs. dacarbazine resulted in FDA approval of trabectedin based on a PFS improvement of 2.7 months over single agent dacarbazine¹⁷. FDA approved trabectedin under the trade name Yondelis® on October 23, 2015 for the treatment of LMS and Liposarcoma.

2.7 Risks/Benefits

Trabectedin as a single agent represents a clear advance in the standard of care for subjects with leiomyosarcoma however with PFS in the 3-5 months range and the OS on the trial used for the approval of trabectedin was 12.4 months, there is clearly a desperate need for improved treatments. Given that immunomodulation clearly occurs as a result of trabectedin, including the elimination of TAM in LMS, there is the potential for synergy with a highly active checkpoint inhibitor such as avelumab.

3.0 STUDY OBJECTIVES

3.1 Study Objectives

3.1.1 Primary Objectives

- To assess the safety and tolerability of the combination of trabectedin and avelumab in subjects with advanced leiomyosarcoma and liposarcoma
- To assess the objective response rate of advanced L-type sarcoma subjects receiving the combination regimen of avelumab and trabectedin

3.1.2 Primary Endpoints

- Safety as measured by CTCAE v5.0.
- Overall Response Rate (PR + CR, best response for each subject) by RECIST v1.1.

3.1.3 Secondary Objectives

- To further explore the clinical activity and safety profile of avelumab and trabectedin as a combination therapy

3.1.4 Secondary Endpoints

- Adverse event profile (based on National Cancer Institute Common Terminology Criteria for Adverse Events [CTCAE] v5.0) for all subjects
- Time to response
- Duration of response
- Progression-free survival (PFS) at 12 weeks, based on RECIST 1.1
- Clinical benefit rate (CR+PR+SD) at 12 weeks, based on RECIST 1.1
- Median overall survival (OS) at 12 months

4.0 TRIAL OVERVIEW

4.1 Study Design

4.1.1 Introduction

This is a Phase I/II, non-randomized, open-label, interventional study of avelumab combined with trabectedin for subjects with advanced L-type sarcoma.

The Phase I stage will evaluate trabectedin (1.5 mg/m²) combined with avelumab (800 mg flat dose). Dose reduction for the trabectedin therapy is permitted after the first cycle. Events which would require a dose reduction of trabectedin are outlined in Section 10, however additional dose reductions may be made at the discretion of the treating clinician down to a lowest possible dose of 1 mg/m². There will be no dose escalation or re-escalation of trabectedin.

4.1.2 Definition of dose limiting toxicity (DLT):

During the phase I portion of the protocol, a DLT will be defined as any grade 3 or higher adverse events, at least possibly-related to protocol therapy, which occur during the first 6 weeks of treatment, with the following specifications and limitations:

- Lab abnormalities that have no clinical sequelae (e.g. febrile neutropenia from low ANC, bleeding from thrombocytopenias etc.) and resolve to grade 1 or better within 7 days will not be considered a DLT.
- Any elevation in total bilirubin > 2x institutional ULN will be considered a DLT.
- Any elevation in AST and ALT over 8x institutional ULN will be considered a DLT.
- ANC <500/ μ L lasting 5 days or more will be considered a DLT.
- Platelets < 25,000/ μ L (grade 4 toxicity) lasting 5 days or more will be considered a DLT.
- Hemoglobin < 7.0 lasting 5 days or more will be considered a DLT.

Additionally, should any grade 5 toxicity (death) occur that is at least possibly-related to treatment (e.g. not easily otherwise explained; for example: a car accident), this will be considered a DLT. In the event of any grade 5 toxicity, enrollment will immediately be put on hold and a data safety monitoring board (DSMB) meeting will be requested immediately.

All clinically significant grade 3 or higher toxicities will be recorded and presented to the DSMB at scheduled meetings. Expected toxicities are those outlined in [Section 10](#). The DSMB will be specifically instructed to consider whether there are increased frequency of known toxicities and to make recommendations accordingly if appropriate. Section 10 summarizes criteria for required dose adjustments.

Enrollment during the first cohort of the Phase 1 portion of the trial will be staggered. The first subject must have received their second dose of both avelumab and trabectedin prior to treatment of the second subject, and the second subject must have received their second dose of both avelumab and trabectedin prior to treating the third subject. In cases where the first subject's second doses of avelumab and/or trabectedin is delayed beyond week 4, either due to trabectedin toxicity or DLT, or is withdrawn or discontinued from the study, the second subject will be allowed to enroll and start therapy. However, the second subject must complete their second dose of trabectedin and avelumab prior to the start of the third subject.

Should 2 or more DLTs be observed in the first 6 subjects, the starting trabectedin dose will be reduced to 1 mg/m² and the Phase 1 will expand to enroll an additional 6 subjects at the new starting dose. Should two or more DLTs be observed in the 6 subjects enrolled at 1 mg/m² the study will go on hold and a DSMB will meet to discuss if there are modifications that could allow the protocol to safely be re-opened. If <2 DLTs are observed in the 6 subjects on the 1.0 mg/m² cohort, enrollment will expand to a third cohort, enrolling an additional 6 subjects at 1.2 mg/m² of trabectedin. If 2 or more DLTs are observed at 1.2 mg/m², then 1.0mg/m² will be determined to be the recommended Phase 2 dose (RP2D). The highest dose with <2 DLTs will be selected for Phase 2 dosing. If one of the first six subjects does not complete the DLT period for a reason unrelated to toxicity (for example withdrawal of consent or tumor progression) that subject may be replaced.

In Phase 2, the study will go on hold and a DSMB meeting will be triggered if more than 30% of subjects have unexpected, probably related SAE's grade 3 or higher that do not resolve to grade 2 within 2 weeks.

In any subsequent Phase 1 cohorts (1.0 mg/m² dosing and 1.2 mg/m² dosing of trabectedin) subjects may be treated concurrently without delay. Prior to beginning Phase 2, each subject on the phase 1 portion must have received their second dose of both avelumab and trabectedin or completed their treatment (e.g. come off study for symptomatic progression).

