4.1.3 Dosing Administration and Schedule

A treatment schedule is provided in Appendix C. Avelumab will be administered via IV infusion over 60 minutes (+/- 10 minutes). Trabectedin is given as an outpatient 24-hour infusion by pump. During week 1, subjects will receive both drugs: avelumab followed by the standard 24-hour infusion of trabectedin. Following avelumab infusions, subjects must be observed for 60 minutes ± 10 minutes (Cycle 1) or 30 minutes ± 5 minutes (Cycle 2+) post-infusion, prior to beginning trabectedin, for potential infusion-related reactions.

Avelumab will be administered every 2 weeks. Trabectedin will be administered every 3 weeks for the first two doses (Week 1 and Week 4), and then every four weeks (Week 7, Week 11,...) moving forward. After Cycle 2 of trabectedin, dosing may extend to every 5 weeks at investigator discretion, for management of trabectedin-associated toxicity only. Delays of trabectedin beyond 5 weeks may be allowed but require written approval from the Sponsor-Investigator.

It should be noted that trabectedin has significant single agent toxicity. Treatment schedule and evaluation of toxicity are discussed in **Section 7.0**.

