4.2 Estimated Accrual

- **Phase 1:** 6 subjects, may expand up to 18
- **Phase 2:** 16 subjects

A minimum of 22, and up to a possible total of 34 subjects are anticipated to receive treatment.

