7.4 Schedule of Treatment Visits

Avelumab will be administered every two weeks starting at Week 1. Dosing may be delayed in response to certain toxicities, as described under Section 10.

Trabectedin will be given every three weeks for Cycle 1 (Week 1) and Cycle 2 (Week 4), and then will be given every 4 weeks (Week 7, Week 11,...). For toxicity management after Cycle 2 (Week 4) Day 1, trabectedin administration may delay to Q5W, as clinically indicated for toxicity management. Delays of trabectedin beyond 5 weeks may be allowed but require written approval from the Sponsor-Investigator.

Administration of either study drug may vary ± 3 days from planned date.

The administration of study drugs during the first 12 weeks (first response assessment timepoint), assuming no dose delays or modifications due to toxicity, is shown below.

The study calendar will be managed in Weeks, with each dose of each drug being noted by a Cycle. For example, assuming there are no deviations from the planned schedule events, Week 1 will have Cycle 1 of avelumab and trabectedin. Week 3 will have Cycle 2 of avelumab, Week 4 will have Cycle 2 of trabectedin, Week 5 will have Cycle 3 of avelumab, Week 7 will have Cycle 4 of avelumab and Cycle 3 of trabectedin, etc. This may change based on dose delays or modifications. Weeks should be counted sequentially regardless of what number the dose of each agent is.

	Week											
Drug	1	2	3	4	5	6	7	8	9	10	11	12*
Avelumab	•		•		•		•		•		•	
Trabectedin	•			•			•				•	

*Response assessment.

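### Phase 2 may open when the last Phase 1 subjects are at about day 22, although DLTs are counted over 6 weeks, so the fewer-than-2-of-6 rule can be read on unfinished windows

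*Combined protocol and SAP*

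**What the plan says.** Section 4.1.2 defines a DLT through events "which occur during the first 6 weeks of treatment". For dose selection it states: "The highest dose with <2 DLTs will be selected for Phase 2 dosing". For the start of Phase 2 it states: "Prior to beginning Phase 2, each subject on the phase 1 portion must have received their second dose of both avelumab and trabectedin". The same sentence accepts, as an alternative, that the subject has finished treatment, with symptomatic progression as the example.

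Under Sections 4.1.3 and 7.4 the second avelumab dose is in Week 3 and the second trabectedin dose in Week 4, so trabectedin sets the date. Section 7.4 adds: "Administration of either study drug may vary ± 3 days from planned date".

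Staggering is written only for subject 1 before 2 and subject 2 before 3 of the first cohort. In the 1.0 and 1.2 mg/m² cohorts "subjects may be treated concurrently without delay". A replacement clause covers a subject among the first six who "does not complete the DLT period for a reason unrelated to toxicity"; replacement is optional.

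Sections 16.1, 16.2 and 16.4 and the Appendix C footnotes do not require the window to be complete before Phase 2 opens. Section 1.0 and Section 16.1 make expansion depend on acceptable toxicity, but neither says how much follow-up that judgement needs.

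**The concern.** Six weeks covers two 3-week trabectedin cycles. The gate is met when the second dose is given, so the last subject may contribute almost no observation after it. A team that follows the text exactly can therefore count DLTs and open Phase 2 while the count can still rise. A subject who leaves early with progression also satisfies the gate on a short window. The step from 1.0 to 1.2 mg/m² has no completion condition at all.

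At stake is the Phase 2 dose. The safety of the combination is the primary objective of Phase 1, and the dose choice rests on this one small count.

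**Working it through.** **The plan's own figure.** The plan gives no operating characteristics for the DLT rule. Its only calculated design figure, the Phase 2 power, does not enter here.

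**Dates.** The second trabectedin dose on day 22 (19 to 25 with the dosing window) means 21 of 42 days seen (18 to 24, or 43% to 57%) and 21 days (18 to 24) still open.

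**Subjects who can still be inside the window at the gate.**
- Even accrual: one or two (below).
- First cohort as written, on planned dates: subjects 3 to 6 may start together, so up to four.
- 1.0 or 1.2 mg/m² cohort: all six.

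**Assumptions.** The documents give no DLT rate for the combination, no onset pattern and no accrual pace. I take:
- true 6-week DLT rates p of 20%, 30% and 40%;
- constant hazard, F(t) = 1 − (1 − p)^(t/42), with t capped at 42;
- even accrual of 22 to 34 subjects (Section 4.2: "A minimum of 22, and up to a possible total of 34 subjects are anticipated to receive treatment") over 24 months (the synopsis gives 2 years as the trial duration) or over 12 months (my assumption).

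**Formula.** P(fewer than 2 DLTs) = Π(1 − Fi) + Σ Fi Π(j≠i)(1 − Fj).

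**Worked case, p = 0.30.**
- Full window: 0.7^6 + 6 × 0.3 × 0.7^5 = 0.118 + 0.303 = 0.420 after rounding.
- Sixth subject at 21 days: F = 1 − 0.7^0.5 = 0.163. P = 0.837 × (0.7^5 + 5 × 0.3 × 0.7^4) + 0.163 × 0.7^5 = 0.837 × 0.528 + 0.163 × 0.168 = 0.469.
- With 18 or 24 days seen instead of 21: 0.477 or 0.462.

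**Even accrual.** The sixth subject is at 21 days, the fifth at 21 plus the spacing, and the fourth has completed in every case.

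| Accrual | Spacing (days) | Fifth subject (days) | P, p = 20% | P, p = 30% | P, p = 40% |
|---|---|---|---|---|---|
| Full window | – | 42 | 0.655 | 0.420 | 0.233 |
| 22 over 24 months | 730/22 = 33.2 | 42 | 0.694 | 0.469 | 0.279 |
| 34 over 24 months | 730/34 = 21.5 | 42 | 0.694 | 0.469 | 0.279 |
| 22 over 12 months | 365/22 = 16.6 | 37.6 | 0.702 | 0.480 | 0.288 |
| 34 over 12 months | 365/34 = 10.7 | 31.7 | 0.712 | 0.494 | 0.302 |

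**Earlier onset.** If two-thirds of DLTs fall by day 21 (linear within each half), the four p = 30% values become 0.456, 0.456, 0.464 and 0.475.

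**Passes that later fail, p = 30%.** The share is (P − P0)/P, where P0 is the full-window value: 10% to 15%, or 8% to 12% with earlier onset.

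**Phase 2 subjects exposed.** Starts in the 21-day gap are 21/spacing = 0.63, 0.98, 1.27 and 1.96. Subjects expected to start at a dose that then fails are (P − P0) × starts:
- p = 30%: 0.031, 0.048, 0.075, 0.144;
- p = 30%, earlier onset: 0.023, 0.035, 0.056, 0.107.

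This counts every start in the gap, although a DLT early in the gap would stop accrual sooner.

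**Clustered starts, p = 30%, 21 days seen.** Four incomplete gives 0.633; six incomplete gives 0.745.

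**The case against.** The strongest reply is that the second-dose condition is a minimum. It sits beside a dose rule that uses a 6-week DLT definition, and the replacement clause makes sense only if a completed window is expected. This is fair. A reader might infer that the protocol directs the team to open Phase 2 at day 22; it does not. Early opening is permitted because nothing forbids it. But a gate is stated, and it is shorter than the window it should protect.

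Second, a reader might infer that late DLTs are lost, or that the rise from 42.0% is a rise in wrong final doses. The documents do not support either. The 2-of-6 rule in Sections 4.1.2 and 16.2 has no cut-off at Phase 2 opening, Section 16.4 convenes the DSMB at 2 of the first 6, and a treatment-related death stops enrolment at once. The pass is provisional. What stands is that these triggers act after Phase 2 subjects may have started. They are also less clear in later cohorts. The Section 16.4 count names only the first six, and a percentage taken within a dose level drops below the 30% trigger after one Phase 2 start (2/7 = 28.6%). The dose rule for 1.2 mg/m² still applies, but the text does not say how it works once Phase 2 is running.

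Third, the size rests on assumptions. Constant hazard ignores that subjects who reach dose 2 have tolerated cycle 1, Section 2.6 reports no cumulative toxicity in one trabectedin trial, and Section 16.2 defines a DLT differently from Section 4.1.2. All of this stands. The earlier-onset case shrinks the effect without removing it. Trabectedin 1.5 mg/m² is also the US standard starting dose (Section 2.6), which limits the concern at that level.

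**Conclusion.** The point holds as a mismatch between a stated gate and the endpoint it serves. The fewer-than-2-of-6 rule can be read while one or two subjects (even accrual), up to four (first cohort as written) or all six (later cohorts) are still inside the window.

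The consequence is small: about 0.02 to 0.14 subjects per dose decision start at a dose that then fails, given a 30% DLT rate, even accrual over 12 or 24 months, and either onset pattern. That range does not cover clustered starts. The 63% and 75% pass probabilities are limits of what the text allows, not expectations.

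The change is still worth making, because Phase 1 exists to settle the safety of the combination and the gap is cheap to close.

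**What to change.** In Section 4.1.2, replace the second-dose gate. Phase 2, and the step from 1.0 to 1.2 mg/m², should open only when every DLT-evaluable subject at the deciding dose has completed the 6-week window or had a DLT. State that a subject who leaves the window early without a DLT, for a reason unrelated to toxicity, is not evaluable. Extend the optional replacement clause from the first six subjects to every Phase 1 cohort, and carry the same wording into Section 16.2.

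No new assessments are needed, because Section 8.2 and Appendix C already require weekly Phase 1 visits through the window. The cost is an accrual pause of up to about 3 weeks (18 to 24 days) per dose decision. A replacement costs more: recruitment plus 6 weeks, or about 53 to 75 days on the spacings above (11 + 42 to 33 + 42). For that reason I would keep replacement optional.
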